10.3.5. Final Study/Early Termination Visit

Subjects who complete the study will have procedures collected as described in Period 2. If a subject withdraws early from the study, the same information will be collected as follows:

- a. A final physical examination will be done.
- b. Sitting vital signs blood pressure, pulse, and temperature will be obtained.
- c. Specimens for safety laboratory tests will be obtained.
- d. The subject will be asked if he/she had any adverse experiences.

If a subject withdraws from the study at any time, either at his or her request or at the Principal Investigator's discretion, the reason(s) for withdrawal will be recorded on the relevant page of the source. All final visit tasks (discharge procedures) will be completed for all subjects who withdraw from the study. Withdrawn subjects may be replaced at the Sponsor's discretion. Subjects withdrawn due to AEs will be monitored until resolution or stabilization of the AE or until 30 days from the initial report of the AE, whichever occurs first.

If a subject is discontinued, the following consistent terminology will be used to capture this information on the CRF:

- Death
- Lost to Follow-up
- Adverse Event
- Non-Compliance with Study Drug
- Physician Decision
- Protocol Violation
- Study termination by Sponsor
- Withdrawal of Consent

10.4. Concomitant Medications, Treatments, and Procedures

The use vitamin K, aspirin or aspirin containing products are prohibited once a subject is entered into this trial. All other concomitant medications are to be recorded.

Any prescription or over-the-counter medication taken during the study will be recorded in the appropriate section of the source document. Any over-the-counter or prescription medications taken during the study will be recorded as a protocol deviation.

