4. SCHEDULE OF PROCEDURES

Evaluation Procedure	Screening Visit	Day of Surgery	Discharge	Safety Follow-ups			Study Exit or Early Withdrawal ⁸
				24 h	Every 24 h until discharge	6 weeks	
Informed Consent	X						
Inclusion/Exclusion Criteria	X						
Diagnosis leading to surgery	X						
Planned procedure	X						
Schwab Curve type and coronal curve magnitude (Cobb angle)	X						
Patient age and demography	X						
Medical/Medication Use History	X						
History of previous spine surgery	X						
Height, Weight, Body Mass Index	X						
Number of units of autologous blood donation	X						
CBC: Hb/Hct/WBC/platelet count (post-autologous blood donation)	X						
Coagulation Profile: PT/PTT/INR	X						
Pregnancy Tests ¹	X	X					
Serum Creatinine	X						
Drug / Alcohol /Tobacco Use	X						
Medication Allergies	X						
Physical Examination	X	X					X
Treatment ID		X					
Details of surgical procedure ²		X					
Surgical complications		X					
Surgery time		X					
Volume of cell saver delivered		X					

Blood Collection ³		X	X				
Location of Hemovac drains		X					
Length of drain use			X				
Length of hospital stay			X				
Peri-operative Blood Loss Assessments ⁴		X	X				
Transfusions ⁵		X					
Complications related to transfusions		X	X				
Urine output ⁶		X					
Tranexamic acid related complications ⁷		X	X	X	X	X	X
Functional recovery assessment		X	X	X	X	X	X
Wound Complications		X	X	X	X	X	X

¹ Females must have a negative serum pregnancy test result at screening and a negative urine test prior to surgery.

²Number of vertebrae fused, number of anchors used, and type of anchors used (screws, hooks, or anchors);
Number and type of osteotomies performed

³ Blood for Hb and Hct measurements will be collected pre-surgery, immediately post-surgery, at 24 h and every 24 thereafter until discharge.

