8.2. Study Endpoints

8.2.1. Primary Endpoints

The primary endpoints of this trial are to assess:

1. Total Blood Loss based on changes in hemoglobin (Blood loss will be calculated by Nadler's and Gross's formulae from the time of admission to hospital until discharge; Hemoglobin and hematocrit concentrations will be measured pre-operatively, post-operatively, and at 24 h and every 24h thereafter until discharge).
2. Incidence of autologous or allogenic blood transfusion, including red blood cells and coagulation components (such as fresh frozen plasma and platelets).

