8.3.3. Withdrawal Criteria

Subjects will be discontinued from the study prematurely if:

1. The subject requests to be withdrawn from the study;
2. A need for a concomitant medication prohibited by the protocol arises;
3. The Principal Investigator decides that it is in the subject's best interest;
4. The subject is incompliant with the protocol;
5. The subject experiences an adverse event that requires premature withdrawal.

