10.3.4. Follow-Up Procedures

Follow-ups on wound complications and on adverse events related to tranexamic acid (such as seizures, DVTs, and PEs) will be conducted minimally every 24 h during hospital stay and at 6 weeks.

Adverse events (AEs) will also be monitored by the investigator and/or designated research staff and spontaneous reporting throughout the study.

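### A subject who needs aspirin or vitamin K must leave the study, after which transfusion recording to discharge and the 6-week DVT/PE/seizure check are no longer required

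*Combined protocol and SAP*

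**What the plan says.** - **Ban.** Section 10.4: "The use vitamin K, aspirin or aspirin containing products are prohibited once a subject is entered into this trial". The section sets no date on which the ban ends.
- **Consequence.** Section 8.3.3 opens with "Subjects will be discontinued from the study prematurely if", and item 2 of its list is "A need for a concomitant medication prohibited by the protocol arises". The exit is from the study, not only from the drug.
- **Exit visit.** Section 10.3.5 lists a physical examination, vital signs, safety laboratory tests and a question about adverse experiences, and adds: "All final visit tasks (discharge procedures) will be completed for all subjects who withdraw from the study". The early-withdrawal column of the Section 4 schedule adds "Tranexamic acid related complications", functional recovery and wound complications. Section 10.3.5 also says: "Withdrawn subjects may be replaced", at the sponsor's discretion.
- **What a retained subject would have had.** Primary endpoint 2 in Section 8.2.1 is "Incidence of autologous or allogenic blood transfusion, including red blood cells and coagulation components", with no time limit. Hemoglobin and hematocrit are taken daily to discharge. Under Section 10.3.4, follow-up for wound complications, seizures, DVT and PE "will be conducted minimally every 24 h during hospital stay and at 6 weeks".
- **Analysis sets.** Section 11.3 keeps every dosed subject in the mITT and safety populations.
- **Other medications.** Section 10.4 first says that other drugs are to be recorded, and then makes any prescription or over-the-counter drug a protocol deviation.

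**The concern.** Vitamin K may be needed for bleeding with coagulopathy, and aspirin for ischemia or to prevent thrombosis. Either need arises after randomization and lies close to what the trial measures. A rule that ends required follow-up at that moment can make missingness depend on outcome.

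Two endpoints are exposed: transfusion incidence between exit and hospital discharge, and DVT, PE or seizure up to 6 weeks. Section 11 has no missing-data rule. Section 11.4.4 compares numbers of patients with events, so a subject who leaves early without a recorded event counts as event-free from then on. The bias could go either way. Placebo exits for bleeding would understate placebo transfusion; active exits for ischemia would understate active thrombosis.

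The rule also protects the patient little after surgery. Study drug is given only before and during surgery, so when the need arises post-operatively no infusion is left to stop, and discontinuation mainly removes data.

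**Working it through.** **1. Is there a route to stop the drug and stay?** Sections 8.3.3, 10.3.4, 10.3.5, 10.4 and 10.7.3, read side by side, contain none.

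**2. What is still required after exit?**

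| Item | Subject who stays | Subject discontinued under item 2 |
|---|---|---|
| Hemoglobin, hematocrit | Daily to discharge | Exit visit at most |
| Transfusions after exit | Recorded | Not required |
| DVT, PE, seizures | Daily in hospital and at 6 weeks | Checked at exit; 6-week check not required |
| Existing adverse events | Followed | To resolution, stabilization or 30 days from first report (10.7.3) |
| New serious events | Reported | Reported if they reach the investigator within 30 days of stopping study drug (10.7.3) |
| New non-serious events | Monitored | Not required |

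The schedule ticks transfusions only on the day of surgery. The endpoint has no such limit, however, and Section 10.5 gives a post-operative hemoglobin trigger for transfusion, so later transfusions count.

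**3. The plan's allowance for loss.** Section 11.2 needs 128 patients and enrolls 150: (150 − 128)/150 = 14.7%, as stated. This covers lost numbers. It does not cover loss that depends on outcome.

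**4. Transfusion incidence.** Inputs: 50 placebo and 100 active (Section 11.2). A subject who exits in hospital without having been transfused has an unknown result.
- Placebo: 1/50 = 2.0 points each; three such subjects, 3/50 = 6.0 points.
- Active: 1/100 = 1.0 point each; three such subjects, 3/100 = 3.0 points.

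Equal counts per arm imply twice the exit rate on placebo. At equal rates the uncertainty is equal: 1 of 50 and 2 of 100 are both 2.0 points. A subject transfused before exit already has the endpoint and contributes no uncertainty.

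**5. DVT/PE, an illustration on assumed inputs.** The documents give no rates. Let a be the share of subjects discontinued before 6 weeks, RR their risk of later events relative to the others (1 to 2), and f the fraction of their later events that is missed:

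share of later events missed = f × a × RR / (1 + a × (RR − 1))

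If all later events are missed, f = 1. If every event is reported as serious through day 30 and timing is even, only days 31 to 42 are missed and f = 12/42 = 0.286.

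| a | f = 1 | f = 0.286 |
|---|---|---|
| 2% (3 of 150) | 2.0–3.9% | 0.6–1.1% |
| 5% | 5.0–9.5% | 1.4–2.7% |
| 10% (15 of 150) | 10.0–18.2% | 2.9–5.2% |

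For example, a = 0.02, RR = 2, f = 1 gives 0.04/1.02 = 3.9%. The result follows a closely, so the table shows sensitivity and is not an estimate. If events cluster early, the right-hand column falls further.

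**6. Blood loss.** Section 11.4.2 makes the 24-hour value the primary measure. It is affected only if the need arises, and the subject exits, before 24 hours.

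**The case against.** The strongest reply is that little is truly lost. A reader might infer that these data are forbidden or certain to be missing. The documents do not support that; they show only that collection is no longer required. Several provisions soften the gap:

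- The discharge procedures required at withdrawal may include a last blood sample and blood-loss assessment. Footnote 8, attached to the early-withdrawal column of the schedule, and Sections 12.3 and 12.4 are not in the available text and could add more.
- A bleeding or ischemic event that prompts the drug is itself an adverse event, and Section 10.7.3 follows its outcome for up to 30 days whatever the reason for exit.
- The synopsis has seizures, DVTs and PEs reported immediately if they occur.
- No visit is scheduled between discharge and 6 weeks, so aspirin use first learned of at 6 weeks costs nothing. The gap concerns use that becomes known earlier.
- Exclusions 8 and 9 in Section 8.3.2 (anticoagulants or abnormal coagulation, fibrinolytic or hematological disease) narrow the need, and Section 11.2 expects little loss to follow-up.

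All of this stands and limits the size. It does not restore the 6-week check or transfusion recording to discharge: the serious-event provision depends on the event reaching the investigator, covers only serious events, and stops 12 days short of 6 weeks.

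A further fair objection is that changing item 2 alone would let the same patient exit under item 3, 4 or 5 (investigator's decision, non-compliance, adverse event). That is right, and the fix is widened to meet it.

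**Conclusion.** The point holds as a gap in required follow-up that can produce informative missing data for transfusion incidence and for DVT, PE and seizures. It is a cheap improvement, not a threat to the trial's main result. The size is 2.0 points (placebo) or 1.0 point (active) of transfusion incidence per untransfused in-hospital exit, multiplied by a number of exits that the documents do not give and that is probably low.

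Three stronger readings are not supported. First, 18.2% is not a projected loss of thrombotic events: it needs 15 of 150 subjects discontinued for this one reason, doubled risk and no serious-event reporting at all, contrary to Section 10.7.3. Second, no material effect on 24-hour blood loss follows. Third, the last sentence of Section 10.4, read literally, makes nearly every surgical patient a deviator, but it does not empty the per-protocol set, because Section 11.3 removes only major violations as judged by a blinded committee. That sentence is a minor inconsistency.

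**What to change.** 1. **Section 8.3.3.** State that for items 2 to 5, that is, for any reason other than the subject's own withdrawal from the study, the study infusion is stopped if still running and the subject stays in the study for all scheduled assessments to discharge and at 6 weeks.
2. **Section 11.** Confirm that these subjects stay in the mITT and safety populations, and tabulate aspirin and vitamin K use by arm. Take the counts from the medication records, because the discontinuation terms in Section 10.3.5 include none for a prohibited drug.
3. **Section 10.4 (minor).** Limit the last sentence to prohibited medications.

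The ban itself can stay. The cost is wording and one table; every assessment retained is already scheduled for all patients. The downside is that outcomes of retained subjects will include any effect of aspirin or vitamin K on bleeding, thrombosis or wound hematoma. The by-arm table shows how often that occurs, and an observed outcome with known drug use is more useful than an unobserved one.

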10.5. Efficacy Assessments

The primary objectives of this trial are to assess:

1. Total Blood Loss (based on hemoglobin changes).
2. Incidence of autologous or allogenic blood transfusion, including red blood cells and coagulation components (such as fresh frozen plasma and platelets).

Total Blood Loss will be determined using Gross's formula¹¹ as follows:

$$V_L = EBV \times \left(\frac{Hct_0 - Hct_f}{Hct_{av}} \right)$$

Where V_L is the volume of total calculated blood loss, EBV is the estimated blood volume from Nadler's formula, Hct_0 is the hematocrit before surgery, Hct_f is the hematocrit at 24 h or discharge/48 h after wound closure and Hct_{av} is the average of Hct_0 and Hct_f .

Nadler's formula¹² is,

Male: $0.3669 \cdot (\text{height})^3 + 0.03219 \cdot (\text{weight}) + 0.6041$, and

Female: $0.3561 \cdot (\text{height})^3 + 0.03308 \cdot (\text{weight}) + 0.1833$,

where, height is in meters and weight is in kilograms.

Secondary efficacy objectives include assessment of:

1. Total measured blood loss (measured intra-operatively and for up to 24 hours post-operatively and every 24 hours up to discharge when the two subfascial drains are removed). Measured Blood Loss will be estimated as 3 times Cell Saver.
2. Number of patients with symptomatic anemia (such as tachycardia, hypotension, presyncope) of <8.0 g/dL hemoglobin, or any hemoglobin <7.0 g/dL, precipitated transfusion. *[Alternatively, allogenic blood transfusion will be considered for hemoglobin <9 g/dL intraoperatively or <8 g/dL post-operatively]*
3. Number of patients with adverse events related to tranexamic acid such as confirmed deep vein thrombosis (DVT), pulmonary embolism (PE), or seizures.
4. Other outcomes will include functional recovery, duration of hospital stay, and wound complications (infections, hematomas, and other complications related with surgery).

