The Total Blood Loss will be estimated based on the hemoglobin content of the blood prior to surgery (mg/dL) and at each of the desired post-surgery time-points (mg/dL). Blood samples for hemoglobin measurement will be collected prior to start of procedure, at the end of the procedure, at 24 h, and every 24 h thereafter until discharge and removal two subfascial drains. Hematocrit analysis will also be conducted on all collected blood samples. The total amounts of fluids infused and amounts of any red blood cell transfusions may be considered, as applicable, in determining the changes in hemoglobin.

In addition, the following data will be recorded:

- Treatment ID
- Details of surgical procedure [Number of vertebrae fused, number of anchors used, and type of anchors used (screws, hooks, or anchors); Number and type of osteotomies performed]
- Any complication prolonging the surgery time or increasing patient blood loss
- Surgery time
- Estimated blood loss peri-operatively (from drainages and absorbent/surgical pads)
- Volume of cell saver delivered
- Units of autologous transfusion and allogenic transfusion
- Units of fresh frozen plasma and platelets administered
- Volume of crystalloids/colloids given

- Urine output
- Location of Hemovac drains and number of drains placed
- Drain output recorded daily
- Length of drain use (uniformly remove drains when output <120 mL/day)
- Length of hospital stay
- Complications of autologous or allogenic transfusion
- Complications of tranexamic acid including renal, hepatic, thromboembolic, and brain/CNS
- Functional recovery assessments will be completed prior to discharge
- Any wound complications for the duration of hospitalization

Follow-up Procedures: Follow-ups on wound complications will be completed minimally at 6 weeks after surgery. Follow-ups on adverse events related to tranexamic acid (such as seizures, DVTs, and PEs) will be reported immediately if they occur.

Adverse events (AEs) will also be monitored by the investigator and/or designated research staff and spontaneous reporting throughout the study.

Confinement: Patients will be confined to the clinic for surgical procedures and recovery as directed by the principal investigator

Study Endpoints: The primary endpoints of this trial are to assess:

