⁴ Blood lost during surgery will be collected by subfascial Hemovac drains at the incision site into canisters containing heparinized saline. Volumes collected will be recorded post-surgery and every 24 h thereafter until discharge. Total measured blood loss will be estimated as 3X cell saver; estimates will be taken off of the anesthesia record. The site will provide a person who will collect blood during consult in the OR and record variables and measurements on the data collection sheet throughout the entire surgery. Final blood loss will be measured post removal of the two subfascial hemovac drains placed during the procedure. The total blood loss will be estimated based on the hemoglobin content of the blood prior to surgery (mg/dL), and post-surgery (mg/dL). Blood samples for hemoglobin measurement will be collected prior to start of procedure, at the end of the procedure, at 24 h, and every 24 h thereafter until discharge and removal of the two subfascial drains. Hematocrit analysis will also be conducted on all collected blood samples. The total amounts of fluids infused and amounts of any red blood cell transfusions will be considered, as applicable, in determining the changes in hemoglobin.

⁵ Units of autologous transfusion and allogenic transfusion; Units of fresh frozen plasma and platelets administered; Volume of crystalloids/colloids given.

⁶ Urine output during surgery.

⁷ Symptoms of thromboembolic complications will be followed and recorded. Either radiocontrast venography or pulmonary scintigraphy will be used to confirm deep vein thrombosis or pulmonary emboli. Any observed seizures during the hospital stay will also be recorded and reported.

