10.3.3. Drug Dosing

Blinded treatments will be administered at an initial dose of 3 mL/kg as a one hour infusion using a calibrated infusion pump prior to start of procedure, and as a 0.3 mL/kg/h infusion during surgery up to a maximum infusion volume of 5 mL/kg. Each treatment will be administered by a calibrated infusion pump. The pump's manufacturer, model, and serial number will be recorded on the CRF. The volume infused remains constant regardless of whether the patient is receiving tranexamic acid or saline.

At the termination of the trial, all unused trial medication must be returned to Exela Pharma Sciences. Instructions for the return of trial medication will be provided by Exela at the completion of the trial.

Blood samples for hemoglobin measurement will be collected prior to start of procedure, at the end of the procedure, at 24 h, and every 24 h thereafter until discharge. Hematocrit analysis will also be conducted on all collected blood samples.

The following data will also be recorded:

- Treatment ID
- Details of surgical procedure [Number of vertebrae fused, number of anchors used, and type of anchors used (screws, hooks, or anchors); Number and type of osteotomies performed]
- Any complication prolonging the surgery time or increasing patient blood loss
- Surgery time
- Estimated blood loss peri-operatively (from drainages and absorbent/surgical pads)
- Volume of cell saver delivered
- Units of autologous transfusion and allogenic transfusion
- Units of fresh frozen plasma and platelets administered
- Volume of crystalloids/colloids given
- Urine output
- Location of Hemovac drains and number of drains placed
- Drain output recorded daily
- Length of drain use (uniformly remove drains when output <120 mL/day)
- Length of hospital stay
- Complications of autologous or allogenic transfusion
- Complications of tranexamic acid including renal, hepatic, thromboembolic, and brain/CNS
- Functional recovery assessments will be completed prior to discharge
- Any wound complications for the duration of hospitalization

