11.3. Populations for Analysis

Up to approximately 150 patients will be enrolled.

The primary analysis population will be a modified Intent to Treat (mITT) population consisting of all subjects receiving an injection of TXA or Placebo.

The secondary analysis population will be a Per Protocol (PP) population consisting of all subjects without major protocol violations (to be

determined by a blinded committee prior to breaking the double-blind code).

The safety population will consist of all subjects receiving an injection of TXA or placebo.

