11.4.2. Analysis of Primary Efficacy Endpoint(s)

The primary efficacy variable will be total blood loss as described in Section 10.1. Since blood loss will be measured up to 24 hours after surgery and over the entire period of hospitalization, the primary measure will be the 24-hour level. Blood loss at later time-points will only be considered significant if the 24-hour measure has also reached statistical significance. Due to the hierarchical structure of this analysis, no adjustment for multiplicity will be performed.

The primary efficacy variables and continuous secondary efficacy variables will be analysed using Analysis of Covariance (ANCOVA) where one factor is treatment (TXA vs Placebo) and the other factor is Surgeon. The initial analysis will include the interaction between the

two factors in order to assess the similarity of effects across surgeons. Significant interaction effects will occur if (for example), TXA works for some surgeons but not for others. The final efficacy analysis will remove the interaction term and control for overall differences between surgeons.

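### The primary Total Blood Loss equation has no term for red cells given before the final hematocrit, and the plan conflicts on whether transfusions count

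*Combined protocol and SAP*

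**What the plan says.** Section 10.5 (Efficacy Assessments) gives the only equation for the primary endpoint: "Total Blood Loss will be determined using Gross's formula", that is V_L = EBV × (Hct0 − Hctf)/Hctav. EBV comes from Nadler's formula and Hctav is the mean of the two hematocrits. Hctf is taken at 24 hours or later, so it follows any red cells given in theatre or soon after. Section 11.4.2 fixes the time point: "the primary measure will be the 24-hour level".

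Three other places bear on red cells.

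- Synopsis (Section 3): "The total amounts of fluids infused and amounts of any red blood cell transfusions may be considered, as applicable, in determining the changes in hemoglobin". The same paragraph describes the endpoint in terms of hemoglobin: "The Total Blood Loss will be estimated based on the hemoglobin content of the blood prior to surgery".
- Section 4, footnote 4: "The total amounts of fluids infused and amounts of any red blood cell transfusions will be considered, as applicable, in determining the changes in hemoglobin".
- Data recorded: "Volume of cell saver delivered" (Section 10.3.3) and "Units of autologous transfusion and allogenic transfusion; Units of fresh frozen plasma and platelets administered" (Section 4, footnote 5).

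The only stated analytic use of cell-saver volume is the threefold multiplier, listed under the secondary measured-loss objective. Section 11.4.2 refers to Section 10.1 for total blood loss, but Section 10.1 covers vital signs and physical examination and adds no rule.

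**The concern.** Gross's equation infers loss from the fall in hematocrit. Red cells given before Hctf raise Hctf and reduce the calculated loss. Section 8.1 makes packed red cells part of standard care in both arms when needed, so this will affect some patients. If placebo patients bleed more and therefore receive more red cells, the calculated loss is lowered more in placebo and the treatment difference shrinks. Section 6.2 cites a meta-analysis reporting fewer transfusions on tranexamic acid, so such an imbalance is plausible, though this trial's rates are unknown. If mean red cells given are equal in both arms, most of the bias disappears.

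The second problem is discretion. One passage makes adjustment optional, another makes it obligatory, the operative section omits it, and none gives a formula, a red-cell content per unit or a time window. Two statisticians could follow this protocol and derive different primary endpoints in a trial meant to support registration. The per-protocol set is to be "determined by a blinded committee prior to breaking the double-blind code"; nothing comparable fixes red-cell handling.

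**Working it through.** **Planning figure.** Inputs from Section 11.2: control mean 2000 mL, SD 1000 mL, 25% reduction (0.25 × 2000 = 500 mL), two-sided 0.05, power 80%. The normal approximation, n = 2 × (1.960 + 0.842)² × (1000/500)², gives 62.8, so 63 per group. The t test gives 63.8, so 64 per group and 128 in total, as stated. Loss allowance: 1 − 128/150 = 14.7%, as stated. Power at 100:50 is 0.82. The sample size is not in dispute; 500 mL is the yardstick below.

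**One patient.** Assume EBV 5000 mL, Hct0 0.40, true loss 2000 mL and one unit containing 200 mL of red cells.

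- Without transfusion, inverting Gross: Hctf = 0.40 × (1 − 0.2)/(1 + 0.2) = 0.267.
- After one unit: Hctf = 0.267 + 200/5000 = 0.307 and Hctav = 0.353.
- Equation alone: V_L = 5000 × (0.400 − 0.307)/0.353 = 1321 mL, so 679 mL is hidden.
- Adding back 200/0.353 = 566 mL gives 1887 mL.

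Over assumed ranges (150–200 mL red cells per unit, EBV 4.2–5.5 L, Hct0 38–42%), one unit hides 410–616 mL at a true loss of 1000 mL and 480–749 mL at 2000 mL.

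**Arm level, by simulation.** Assumptions: 300,000 patients per arm; lognormal loss with means 2000 and 1500 mL; SD 1000 mL in both arms, or CV 50%; EBV mean 4.8 L (SD 0.7); Hct0 mean 40% (SD 3); hematocrit falling as exp(−V/EBV); 180 mL red cells per unit. Units are given below hematocrit 21, 24 or 27%, standing for the hemoglobin values 7, 8 and 9 g/dL in Section 10.5 at Hct = 3 × Hb. These thresholds are inputs only and none is endorsed. The true difference is 500 mL; with no red cells given, Gross reads about 478 (SD 1000) or 470 (CV 50%).

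| Units only, given after bleeding | 21% | 24% | 27% |
|---|---|---|---|
| SD 1000: equation alone, mL | 404 | 329 | 226 |
| SD 1000: with add-back, mL | 456 | 441 | 420 |
| SD 1000: gap in mean units | 0.09 | 0.20 | 0.36 |
| CV 50%: equation alone, mL | 347 | 260 | 157 |
| CV 50%: with add-back, mL | 430 | 410 | 384 |
| CV 50%: gap in mean units | 0.15 | 0.27 | 0.44 |

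Simulation error is a few mL. If units are given during bleeding instead, the equation-alone figures change by at most 2 mL, with unit gaps of 0.10–0.54. Across both timings the two versions differ by 53–287 mL, or 48–289 mL with 150 or 200 mL per unit.

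- Cell saver only (one sixth or one third of the loss returned at hematocrit 40–60%): 80–375 mL alone against 353–488 with add-back.
- Both together: 80–355 against 353–488. The effects do not simply add, because reinfusion often keeps hematocrit above the threshold.
- One unit to every patient in both arms: 429 or 419 mL on the equation alone.
- Add-back is closer to 500 mL in all 108 scenarios (12 units only, 24 cell saver only, 72 combined).

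**Power and false positives** (50 placebo, 100 active; t test instead of the planned surgeon-adjusted model). Equation-alone power is below 0.80 in 9 of 108 scenarios, lowest 0.57; with add-back the lowest is 0.82. Under no effect, each version alone gives 4.9–5.3% false positives. Taking the better of the two after unblinding would give 5.5–9.1%.

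**The case against.** The strongest reply is that the error is conservative. The bias is toward no difference, false positives do not rise, and transfusion incidence is a separate listed primary endpoint. Power also mostly survives, because transfusion compresses the spread: the equation-alone SD falls to about 430–680 mL. With the protocol's SD of 1000 mL, units-only power is 0.94, 0.93 and 0.82 at the three thresholds. All of this stands, and a calculation that shrank the difference while holding the SD at 1000 mL would overstate the loss of power. It does not rescue the effect estimate. Section 11.4.2 makes total blood loss the primary efficacy variable, and Section 11.2 sizes the trial on it.

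The schedule footnote also says transfusions will be considered, so the fully unadjusted reading goes against one passage. True, but that footnote names no method, the synopsis makes adjustment optional and Section 10.5 omits it.

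The larger distortions do need strong inputs. The 27% threshold is applied throughout, although 9 g/dL is an intraoperative value in the protocol. The one-third cell-saver share borrows a secondary-endpoint multiplier, and at hematocrit 60% it returns about 62% of the lost red cells. The 80 mL low end depends on that and should not be read as an expected value.

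Section 8.4 withholds treatment codes from site and sponsor trial personnel until the trial and final data review are complete. That is partial protection, but Section 8.1 leaves the sequence open to the statistician who generates it, and no passage dates the choice of derivation. The 5.5–9.1% figure shows what selection after unblinding could do; nothing suggests it is planned.

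Finally, the hemoglobin wording is minor, since both quantities come from the same samples. Fluids are a fair challenge and are dealt with under the fix.

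**Conclusion.** The concern holds and needs correcting before unblinding. That the equation lacks a red-cell term, that the two transfusion statements conflict without a rule, and that cell-saver reinfusion is unaddressed (rather than contradicted) all rest on the text alone, with high confidence. The sizes are illustrative: transfusion rates, red-cell content per unit and cell-saver hematocrit are assumed, because the documents give none. Under those assumptions, gaps of only 0.09–0.54 mean units between arms reduce a true 500 mL difference to 157–404 mL on the equation alone. The direction depends on placebo patients receiving more red cells. The harm is a biased effect size and a discretionary primary endpoint. It is not a general loss of power, and not a higher false-positive rate unless the version is chosen after unblinding.

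**What to change.** In Section 10.5 define Total Blood Loss = V_L + (red-cell volume given between the Hct0 and Hctf samples)/Hctav, covering allogeneic, autologous and cell-saver red cells. Prespecify the red-cell content per unit and an assumed cell-saver hematocrit. For the 24-hour primary measure, count only product given before that draw. Replace the conflicting sentences in the synopsis and in Section 4, footnote 4 with this rule, stating that it works on hematocrit and that infused fluids do not enter separately. Report unadjusted Gross and varied red-cell content as sensitivity analyses, summarise infused fluid volume by arm, and fix everything before unblinding.

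The cost is wording plus one derived variable. Units and cell-saver volume are already recorded, but cell-saver hematocrit is not listed and must be assumed. The schedule table, in the copy available, marks transfusions on the day of surgery only, so later units given before the 24-hour draw may need a collection point with times.

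Two limits remain. Add-back reduces the bias without removing it (353–488 mL against 500 in these scenarios), because transfusion also raises the divisor Hctav. Leaving fluids out assumes similar volume status in both arms at the draw: an equal 5–10% offset moves the difference by 4–10 mL, but a 5% excess in placebo alone raises it by about 220 mL. That is why the fluid summary by arm is needed.
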